8.1 Overview of Safety Analysis Methods

All safety analyses will be carried out using the safety sample defined in Section 4 unless otherwise noted. Missing safety information will not be imputed. Safety will be analyzed separately in Phase 1a, Phase 1b, and Phase 2 through the reporting of adverse events (AEs).

Listings will be prepared for all safety measurements. All listings will be sorted in order of subject identifier and time of assessment.

8.2 Primary Adverse Events Endpoints

All AEs will be classified by system organ class (SOC) and preferred term, according to a standardized thesaurus (Medical Dictionary for Regulatory Activities [MedDRA] version 18.1). The severity of AEs will be classified, as applicable, using the following grading scales:

- The National Cancer Institute's Common Toxicity Criteria for Adverse Events version 4.03.
- Grading scale of local reactions related to the Nasal Allergen Challenge or skin testing.
- Declines in PEF during the Nasal Allergen Challenge visit
- Grading system of severity of anaphylaxis

Each AE is entered on the electronic case report form (eCRF) once at the highest severity.

An overall summary table will be developed to report the number of events and the number and percentage of subjects having at least one event in the following categories:

- AEs
- AEs indicated as serious
- AEs that lead to study drug discontinuation
- AEs with an outcome of death
- AEs that were reported as being related to a study drug, including instances where PEF declined by more than 20% from baseline
- AEs reported by maximum severity on each applicable grading scale.

Summary tables will present the total number of events as well as the number and percentage of subjects experiencing the events. If a subject experiences the same AE on multiple occasions, the event will be counted once for each occurrence when reporting the number of AEs. When reporting the number of subjects experiencing the events, a subject will only be counted once if they experience an event within the particular SOC or preferred term. Percentages will be based on the number of subjects in the safety population.

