8.3. Challenge Visit

Participants who are deemed eligible based on results from tests conducted at the Screening Visit will be invited to proceed to the Challenge Visit in Phase 1a and Phase 2.

The following procedures, assessments, and laboratory measures will be conducted:

1. Concomitant medications
2. Adverse events
3. Assessment of nasal and pulmonary symptoms (including spirometry)
4. Brief Physical Exam - includes Vital signs, height, weight and nasal and lung exam (or as specified in the MOP for Protocol ICAC-27)
5. Urine pregnancy test (female participants; if more than 28 days after the screening visit)
6. Initial nasal rinses – approximately 200mcl of isotonic saline solution (2 sprays) will be sprayed into each nostril and the participant will be asked to blow their nose; this process will be repeated 3 times (as specified in the MOP for Protocol ICAC-27). The fluids from the 2nd and 3rd rinses will be collected and processed for analysis as specified in the MOP for Protocol ICAC-27 – the outcomes from these fluids will be considered baseline for the ensuing nasal challenge procedure. A nasal rinse will be repeated 10 minutes after the diluent control is administered and after each dose of allergen during the NAC, as specified in the MOP for Protocol ICAC-27.
7. Nasal symptoms – TNSS and VAS and will be assessed pre and post the initial nasal rinses, and then 10 -20 minutes after each NAC dose administration and before the nasal rinse. (as specified in the MOP for Protocol ICAC-27) If the participant does not qualify for the Challenge because of the TNSS score, they may be rescheduled as per the MOP for Protocol ICAC-27.
8. Peak nasal inspiratory flow (PNIF) - assessed pre and post the initial nasal rinses, and then 10-20 minutes after each NAC dose administration (as specified in the MOP for Protocol ICAC-27)

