8.9. Visit Windows

Study visits should take place within the time limits specified below: the designated visit windows (*i.e.* $+- n$ days) for each scheduled visit are also indicated on the Schedule of Events. Additional details are provided in the MOP for Protocol ICAC-27.

The Challenge Visit should be conducted within 2 months of the screening visit. Participants unable to return for the Challenge Visit within 2 months of the Screening Visit will need to have the medical history, physical exam and urine pregnancy test (if applicable) repeated prior to initiation of the NAC. Participants may be reevaluated up to a maximum of 2 times for the Phase 1a and Phase 2 Challenge Visits if they are ineligible due to nasal symptoms or other reversible illness if their condition improves within 2 months of the Screening Visit.

A Follow-Up Phone Visit should occur approximately 24 hours after the end of a Challenge Visit (as described in the MOP for Protocol ICAC-27). In a subset of sites in Phase 1a, Phase 1b, and Phase 2, a Follow-Up Clinic Visit may occur in lieu of the phone call (see MOP for Protocol ICAC-27 for details). A Follow-Up Clinic Visit should occur 6 to 10 days after the Challenge Visit for participants who have agreed to participate in the mechanistic blood draw. Another Follow-up Phone Visit should occur 6 to 10 days following a challenge if the participant is not seen at the study site at this time (as described in the MOP for Protocol ICAC-27).

The optional Phase 2 30-day Follow-Up Visit should occur 30 days after the Challenge Visit (as described in the MOP for Protocol ICAC-27).

The Phase 1b Repeat Challenge Visit should be conducted within 30-365 days after the Challenge Visit. Participants may be reevaluated up to a maximum of 3 times for the Phase 1b Repeat Challenge Visit if they are ineligible due to nasal symptoms or other reversible illness if their condition improves during the 365 days after their initial Challenge Visit.

The Phase 1b 30-day Follow-Up Visit should occur 30 days after the Repeat Challenge Visit (as described in the MOP for Protocol ICAC-27).

9. Mechanistic Assays

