Blood samples will be drawn prior to the NAC at either the Screening visit or at the Challenge Visit, depending upon the method of recruitment. Additional blood will be drawn once in all phases 6-10 days after the Challenge Visit (or as specified in the MOP for Protocol ICAC-27). In Phase 1b, participants will undergo an additional blood draw at the Challenge Visit approximately 6 hours after the initiation of the challenge. In Phase 1b and Phase 2, participants will undergo an additional blood draw 30 days after the Challenge Visit, which will be optional for Phase 2 participants. These mechanistic blood samples will be evaluated for T-cell epitope repertoire against cockroach allergens. Nasal secretions will be collected during Challenge Visits. These secretions will be assayed for biomarkers to include tryptase and albumin. In a subset of sites in Phase 1a, Phase 1b, and Phase 2, additional blood will be drawn once immediately preceding the NAC and once 24-72 hours after the NAC for additional mechanistic studies focusing on changes in chemokines and other biomarkers in blood and nasal secretions. Details of these studies are specified in the MOP for Protocol ICAC-27.

10. Biospecimen Storage

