	
at least 2 participants:
 
a. Anaphylactic reaction grade 2 or higherb. Reduction of FEV1 by more than 15% from baseline and/or reduction of PEF by more than 20% from baseline and inability to perform spirometry due to administration of rescue medications in Phase 1 or Phase 2.
--	---

2. Introduction

This statistical analysis plan includes pre-planned analyses related to the study objectives outlined in the protocol.

3. General Analysis and Reporting Conventions

The following analyses and reporting conventions will be used:

- Categorical variables will be summarized using counts (n) and percentages (%) and will be presented in the form “n (%).” Percentages will be rounded to one decimal place.
- Numeric variables will be summarized using n, mean, standard deviation (SD), median, minimum (min), maximum (max). The min/max will be reported at the same level of significance as original data. The mean and median will be reported at one more significant digit than the precision of the data, and SD will be reported at two more significant digits than the precision of the data.
- The median will be reported as the average of the two middle numbers if the dataset contains an even number of observations.
- Test statistics including t and z test statistics will be reported to two decimal places.
- P -values will be reported to three decimal places if greater than or equal to 0.001. If less than 0.001, the value will be reported as “<0.001.” A p -value can be reported as “1.000” only if it is exactly 1.000 without rounding. A p -value can be reported as “0.000” only if it is exactly 0.000 without rounding.

If departures from these general conventions are present in the specific evaluations section of this SAP, then those conventions will take precedence over these general conventions.

4. Analysis Samples

The safety population will include all study participants who received the initial dose during the Challenge Visit. This population breaks down further into the Phase 1 adult and Phase 2 child cohorts.

5. Study Subjects

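### Phase 1b adverse event percentages are based on a safety population that keeps adults who were never re-challenged

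*SAP*

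**What the plan says.** SAP 8.1 names three safety analyses: "Safety will be analyzed separately in Phase 1a, Phase 1b, and Phase 2". It also names the sample for all of them: "All safety analyses will be carried out using the safety sample defined in Section 4 unless otherwise noted". SAP 8.1 to 8.3 note no exception for Phase 1b.

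The sample is in SAP Section 4: "The safety population will include all study participants who received the initial dose during the Challenge Visit". Its only subdivision is by cohort: "This population breaks down further into the Phase 1 adult and Phase 2 child cohorts". SAP 8.2 then gives the denominator for the adverse event tables: "Percentages will be based on the number of subjects in the safety population".

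Protocol 13.4.1 defines the population in the same way, says that it is the only one, and applies it to every analysis.

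Protocol 3.1 expects all 10 adults to return for the repeat challenge. Other sections allow for fewer. Protocol 11.1 treats an adult who refuses Phase 1b as having completed the study. Protocol 4.2, 4.3 and 8.4 set separate entry criteria for Phase 1b, and some adults may fail them.

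**The concern.** An adverse event percentage for a challenge should have as its base the people who received that challenge. For Phase 1a and Phase 2, the Section 4 definition gives that base. For Phase 1b it does not, because membership was settled at an earlier visit. An adult who does not return can add nothing to the Phase 1b numerator but is still counted in the denominator.

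Safety is one of the two primary outcomes, and protocol 13.4.2 assesses it through the rate of related adverse events and serious adverse events. Phase 1b is the study's only source of such rates after a second challenge. A base that is too large makes those rates look lower than they were.

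**Working it through.** **Which set does the SAP's rule select for Phase 1b?** The protocol mostly keeps the two visits apart. Section 8.3 says eligible participants "will be invited to proceed to the Challenge Visit in Phase 1a and Phase 2", and 8.9 says "The Phase 1b Repeat Challenge Visit should be conducted within 30-365 days after the Challenge Visit". On that usage, the Section 4 population is fixed before Phase 1b starts. Protocol Section 9 uses the term more loosely: "In Phase 1b, participants will undergo an additional blood draw at the Challenge Visit". The looser usage does not change the set. Every adult in Phase 1b was already dosed in Phase 1a, so counting the repeat visit as a Challenge Visit adds nobody and removes nobody. Under either usage, the Phase 1b denominator is the whole adult cohort.

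**Inputs**
- Adults in the Section 4 population: 10 (protocol 3.1, assuming all enrolled adults receive the initial dose in Phase 1a).
- Adults re-challenged in Phase 1b: m. The plan is 10. The documents give no other figure, so m = 9, 8 and 7 are assumptions for illustration.
- Adults with at least one event in Phase 1b: x, taken as 1 or 2 for illustration.

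**Formulas.** SAP percentage = x/10. Percentage among those re-challenged = x/m. Ratio of the first to the second = (x/10)/(x/m) = m/10.

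| m | Ratio m/10 | x = 1: SAP vs re-challenged | Gap (points) | x = 2: SAP vs re-challenged | Gap (points) |
|---|---|---|---|---|---|
| 10 | 1.0 | 10.0% vs 10.0% | 0 | 20.0% vs 20.0% | 0 |
| 9 | 0.9 | 10.0% vs 11.1% | 1.1 | 20.0% vs 22.2% | 2.2 |
| 8 | 0.8 | 10.0% vs 12.5% | 2.5 | 20.0% vs 25.0% | 5.0 |
| 7 | 0.7 | 10.0% vs 14.3% | 4.3 | 20.0% vs 28.6% | 8.6 |

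**Scale.** The documents state no Phase 1b safety rate, so there is no figure of theirs to reproduce on this point. The nearest is the table of exact 95% intervals for 10 subjects in protocol 13.6. All 11 rows agree, to rounding, with the Clopper-Pearson formula. For 1 of 10 the interval is 0.003 to 0.45, far wider than any gap in the table above.

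If no adult has an event, the percentage is 0 on either base, but what can be ruled out is not the same. The exact 95% upper limit is 30.8% with 10 exposed and 36.9% with 8. The SAP plans no such interval for adverse events; the comparison only shows what the choice of base implies.

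**The case against.** The best defence is that a separate Phase 1b analysis naturally covers Phase 1b participants. The protocol treats Phase 1b as its own enrolment step, with its own criteria in 4.2 and 4.3, and a sensible programmer might use that set. This shows that the intention may be sound. It does not remove the written rule: SAP 8.1 defaults to the Section 4 sample, no exception follows, and protocol 13.4.1 says there is only one population.

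The other objections limit the size of the point, and they stand. With all 10 adults back there is no error. SAP 8.2 shows counts beside percentages, and SAP 5.1 tabulates completion of each visit, so a careful reader could recover m. The stopping rules in protocol 11.5 count events, and protocol 3.1 makes progression to Phase 2 independent of Phase 1b.

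A reader might infer more in three ways, none of which the documents support.
- *That the adults wrongly kept would mostly be those who reacted in Phase 1a.* Some Phase 1b exclusions do follow Phase 1a reactions (4.2, 4.3), so the loss may be informative. Many others do not, such as refusal, pregnancy, medication washout, loss to follow-up or a different initial TNSS. The mix of reasons is not given.
- *That the base is all 35 participants.* SAP 8.2 alone could be read so, but Section 4 splits the population by cohort and 8.1 analyses the phases separately. The adult cohort is the natural reading.
- *That the related-event row in SAP 8.2 also counts PEF falls of more than 20% without the protocol's FEV1 condition.* The row is limited to adverse events reported as related. SAP 8.2 also adopts the PEF grading scale, and the footnote to Table 12.3.1b in the protocol says a fall is not an adverse event when the spirometry it prompted shows FEV1 of at least 85% of baseline. The natural reading inherits that condition, so at most the wording could be clearer.

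**Conclusion.** The point holds and is minor. As written, the SAP understates Phase 1b safety percentages by the factor m/10 whenever fewer than 10 adults are re-challenged. For m between 7 and 9 and one or two affected adults, the gap runs from 1.1 to 8.6 percentage points. At m = 10, which is the plan, it is zero.

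This rests on 10 adults entering the safety population in Phase 1a and on assumed values of m and x. The effect is confined to descriptive Phase 1b tables. The PEF wording is not an error and forms no part of this conclusion.

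**What to change.** In SAP Section 4 and 8.2, state that Phase 1b safety percentages use the subset of the safety population that received the initial dose at the Repeat Challenge Visit. Amend protocol 13.4.1 so that its single-population statement allows this subset. The new base corrects the denominator; it does not remove any selection in who returns, so the Phase 1b tables should be read beside the reasons for not being re-challenged.

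As an optional clarification, SAP 8.2 could say that the related-event row counts only PEF declines that are adverse events under protocol 12.3.1, with attribution as in 12.3.4.

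The cost is one sentence in each document. No data collection or clinical rule changes. Phase 1b percentages may look less favourable if some adults do not return.

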3.1. Description of Study Design

This is a multi-center, open label pilot study to assess the safety and determine the feasibility of cockroach nasal allergen challenge (NAC) in children with asthma. This pilot study will occur in two phases. Phase 1 will enroll 10 cockroach sensitive adults with asthma who will undergo a nasal allergen challenge with increasing doses of cockroach allergen. This phase will consist of two parts, Phase 1a and Phase 1b. In Phase 1a, the cockroach sensitive adults will undergo the initial NAC. In Phase 1b, the adult participants will undergo a repeat challenge 30-365 days after the Phase 1a NAC. The purpose of Phase 1b is to assess reproducibility of the NAC with cockroach allergen in a population with asthma. Phase 2 will enroll 25 cockroach sensitive children with asthma who will undergo a NAC with increasing doses of cockroach allergen. Progressing to Phase 2 will not be dependent upon the results of Phase 1b, and Phase 2 will proceed immediately after the completion of Phase 1a. After the completion of Phase 1a, the primary outcome data (positive response to NAC, defined as TNSS \geq 8 out of 12 or a sneezing score of 3) for the participants in Phase 1a will be reviewed to determine the optimal dose range to be used in Phase 2. Considerations for choosing the most appropriate dose range will include tolerability and the aim of eliciting a threshold of nasal symptoms. The investigators planned to use the results of the primary outcome analysis (Section 13.4.2) to determine the optimal dose to be used in Phase 2, with the combination of the optimal dose, one dose above, and 2 doses below the optimal dose to be selected as the four doses to be used in Phase 2. However, an optimal dose was not determined in Phase 1a. It was noted that no adult reacted to the first dose of allergen (challenge dose 2).

Phase 2 will enroll 25 cockroach sensitive children with asthma, ages 8-14 years, who will undergo a nasal allergen challenge with all 8 allergen doses used in Phase 1a in at least the first 5 participants to ensure a similar pattern of response. If none of these 5 children react to the first dose of allergen (challenge dose 2), then that dose will be dropped from subsequent challenges. The threshold for a positive response to the NAC in Phase 2 will be defined as a TNSS \geq 6; the sneezing score of 3 will remain the same.

[figure not shown]

Figure 3.1 Cockroach Nasal Allergen Challenge Study Design

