6.1.2. Dosage, Preparation, and Administration

Dilutions of the German cockroach allergenic extract needed for NAC dose escalation will be prepared by the site research pharmacy.

Participants will receive escalating doses of glycerinated German cockroach allergenic extract administered via the intranasal route. Each dose will be administered as a nasal spray with the use of a nasal drug delivery system (LMA/Teleflex, San Diego, CA), which delivers 0.1 mL per activation (spray). One spray will be delivered in each nostril for a total delivered volume of 0.2 mL. Nine doses will be given. Dose 1 will be a diluent control. Doses 2 through 9 will have a Bla g 1 dose range of approximately 0.002 mcg to 5 mcg.

All 8 allergen doses will be used in the first 5 children in Phase 2 to ensure a similar response pattern to that seen in the adults. If, like in the adults in Phase 1, none of these 5 children react to the first allergen dose, this dose will be dropped from the subsequent challenges. The threshold for a positive response to the NAC in Phase 2 will be defined as a TNSS ≥ 6 ; the sneezing score of 3 will remain the same.

The proposed NAC dose escalation for Phase 2 was reviewed and approved by the NIAID Allergy and Asthma DSMB.

Complete details of the dilutions can be found in the MOP for Protocol ICAC-27, which is based on the DAIT Pharmacy manual.

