13.4.2 Primary Analysis of Primary Outcomes

The first primary objective of this analysis is to estimate a probability of positive response at each dose, defined as reaching a sneezing score of 3 or a TNSS of ≥ 8 in Phase 1 or a TNSS of ≥ 6 in Phase 2. The probability of reaching a positive response will be estimated using the percentage of responses in subjects at each of the 9 doses. Although a participant will stop receiving doses once they have reached a sneezing score of 3 or a TNSS of ≥ 8 in Phase 1 or a TNSS of ≥ 6 in Phase 2, it is assumed that they would continue to respond for the remaining doses. Therefore, if 7 people respond prior to Dose 5, 3 will be tested at Dose 5, and the proportion presented for Dose 5 would be $(7 + \# \text{ responders at Dose 5})/10$. Associated exact 95% confidence intervals will be estimated using the Clopper-Pearson method.

The second primary objective of this analysis is to assess if intranasal delivery of cockroach allergen via a nasal allergen challenge is safe. This will be done by determining the rate of related adverse events and serious adverse events in the course of treatment. Frequency of AEs and SAEs will be tabulated by event, organ, seriousness, severity, and treatment relatedness.

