	cockroach allergen in a population with asthma. The data from Phase 1a will be used to identify a range of doses that is safe and elicits a threshold of nasal symptoms (TNSS ≥ 8 or a sneezing score of 3). Phase 2 will enroll 25 cockroach sensitive children with asthma ages 8-14 years who will undergo a nasal allergen challenge using the dose range identified in Phase 1a. The threshold for a positive response to the NAC in Phase 2 will be lowered to a TNSS ≥ 6 ; the sneezing score of 3 will remain the same.
Primary Outcomes	
 1. Prevalence of a positive response to NAC, defined at each dose as any sneezing score of 3 or a Total Nasal Symptom Score (TNSS) ≥ 8 out of 12 in Phase 1 or a TNSS ≥ 6 out of 12 in Phase 2. 2. The number of reported adverse events and serious adverse events, including their severity, seriousness, and relatedness
Secondary Outcomes	
 1. Number of Sneezes 2. TNSS – highest score out of all doses received 3. TNSS – change from baseline 4. Change in PNIF from baseline 5. Change in PEF from baseline 6. Visual Analog Scale (VAS) - change from baseline 7. Change in tryptase in nasal secretions 8. Change in albumin in nasal secretions
Exploratory Outcomes	
 1. Change in chemokines and other biomarkers in nasal secretions 2. Change in cockroach-specific T-cell epitopes in peripheral blood
Accrual Objective	35 (Phase 1 - 10 adults, Phase 2 - 25 children)
Study Duration	1 year
Treatment Description	Participants will receive escalating doses of glycerinated German cockroach allergenic extract administered via the intranasal route.
Inclusion Criteria	
Individuals who meet all of the following criteria are eligible for enrollment as study participants for Phase 1a and Phase 2:
 
 1. Subject and/or parent guardian must be able to understand and provide informed consent. 2. Male or female adults, 18 through 55 years of age at recruitment (Phase 1) or male or female children, 8-14 years of age at recruitment (Phase 2).

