7.2 Secondary Efficacy Outcomes

Participants stopped receiving doses once they reached a positive response, so all doses were not observed for each subject. This truncated nature of the data violates assumptions of standard statistical tests. In light of this issue, we will use descriptive statistics to assess secondary study hypotheses instead of formal hypothesis tests.

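### Response is estimated at each dose, but adverse events are tabulated only by phase, so no planned analysis ties safety to dose or to the number exposed

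*SAP*

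**What the plan says.** The aim is framed by dose. The SAP synopsis (Study Design) says: "The data from Phase 1a will be used to identify a range of doses that is safe and elicits a threshold of nasal symptoms". Protocol 3.1 adds: "Considerations for choosing the most appropriate dose range will include tolerability and the aim of eliciting a threshold of nasal symptoms". Positive response and adverse events (AEs) are both primary outcomes (Protocol 3.2).

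Response has an analysis to match. Protocol 13.4.2 and SAP 7.1.4 to 7.1.5 estimate it at each of the 9 doses with Clopper-Pearson intervals. Earlier responders are counted as responders at every later dose, so the denominator stays at the full cohort.

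Safety has no by-dose counterpart:

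- SAP 8.1 separates AEs by Phase 1a, 1b and 2.
- Protocol 13.4.2: "Frequency of AEs and SAEs will be tabulated by event, organ, seriousness, severity, and treatment relatedness".
- SAP 8.2 adds discontinuation, death and maximum severity. It counts PEF falls beyond 20% among related events, again without dose. On denominators: "Percentages will be based on the number of subjects in the safety population".
- SAP 4: "The safety population will include all study participants who received the initial dose during the Challenge Visit".
- Protocol 6.1.2: "Dose 1 will be a diluent control".

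SAP 7.2 recognises that exposure is truncated: "Participants stopped receiving doses once they reached a positive response, so all doses were not observed for each subject". It draws the consequence for the secondary outcomes only.

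**The concern.** A dose range has two halves, response and tolerability, and only the first is analysed at the level at which the question is asked. The AE denominator is fixed at everyone who started the challenge, while the number exposed falls as escalation proceeds. An event at a high dose is therefore averaged over people who never received that dose, and an absence of events looks equally well supported at every dose.

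The AE tables also miss part of tolerability. A challenge may end because symptoms become intolerable (Protocol 8.3, item 11), yet rhinitis symptoms below the levels of Table 12.3.1a are not AEs (Protocol 12.3.2). Reasons for early termination are summarised by cohort (SAP 5.1), not by the dose at which the challenge stopped.

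At stake is the closing statement of a pilot whose purpose (Protocol 1.1) is to settle safety and dosing for possible use in a later immunotherapy trial. The upper end of the range is where the fewest people are likely to have been exposed.

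**Working it through.** **Inputs**

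- Cohorts: 10 adults and 25 children (both synopses).
- Doses: 9, of which Dose 1 is diluent and 8 are allergen (Protocol 6.1.2).
- Attrition: 7 of 10 respond before Dose 5, so 3 receive it (illustration in SAP 7.1.4 and Protocol 13.4.2).
- Interval: two-sided 95% Clopper-Pearson, which the plan uses for response. The plan gives no interval for AEs.

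**Formulas**

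For x events in n people, the lower limit is the 0.025 quantile of Beta(x, n − x + 1) and the upper limit is the 0.975 quantile of Beta(x + 1, n − x). With x = 0 the lower limit is 0 and the upper limit is 1 − 0.025^(1/n).

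**Reproducing the plan's table (Protocol 13.6)**

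- 0/10: 1 − 0.025^(1/10) = 1 − 0.6915 = 0.3085 (printed 0.31)
- 1/10: 0.0025 to 0.445 (printed 0.003 to 0.45)
- 5/10: 0.187 to 0.813 (printed 0.19 to 0.81)
- 10/10: lower limit 0.6915 (printed 0.69)

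All 11 rows agree with the printed figures.

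**No events, by number exposed at the dose**

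| Exposed | Upper 95% limit | Source of the number exposed |
|---|---|---|
| 10 | 30.8% | whole adult cohort |
| 5 | 52.2% | assumed |
| 3 | 70.8% | the documents' Dose 5 illustration |
| 2 | 84.2% | assumed |
| 1 | 97.5% | assumed |
| 25 | 13.7% | whole child cohort |
| 15 | 21.8% | assumed |

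**One event at a dose that 3 adults received**

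- Among those exposed: 1/3 = 33.3% (0.8% to 90.6%).
- As SAP 8.2 would report it: 1/10 = 10% (0.3% to 44.5% if an interval were attached).

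**Chance of seeing any event, for an assumed true risk of 20%**

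- 10 exposed: 1 − 0.8^10 = 89%.
- 3 exposed: 1 − 0.8^3 = 49%.

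**The case against.** There is a good deal to say for the plan.

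- **The safety objective is worded for the procedure.** The second objective in Protocol 2.2 and the second analysis in 13.4.2 ask whether the challenge is safe over its course. For a procedure titrated to response, everyone challenged is the right denominator. This stands. The phase-level tables are not an error and should stay.
- **The data will be available.** A reader might infer that a safe range could not be identified, or that no output shows how many people received each dose. The documents do not support either. SAP 8.1 plans safety listings in time order for each subject. SAP 7.2.3 lists and graphs PEF at each dose for each subject. SAP 7.1.5 tabulates TNSS at each dose, and SAP 3 requires n in numeric summaries. With 35 participants, someone could piece this together by hand. What is missing is a planned link between those numbers and the AEs. Neither document says that dose at onset is recorded.
- **The decision on children has its own record.** A reader might infer that the phase-level percentages justified giving children the full range. Nothing shows this. Protocol 3.1 reports that Phase 1a determined no optimal dose, and Protocol 6.1.2 says the DSMB approved the Phase 2 escalation. The DSMB's planned reviews include a listing of all AEs and SAEs (Protocol 12.8.2.1).
- **The contrast in limits is calculated here.** The SAP plans no AE interval, so 31% is a yardstick and not a figure the sponsor would publish. This stands. The 10% against 33% comparison does not depend on it.
- **A by-dose rate is not a clean dose-specific risk.** Doses follow at about 20-minute intervals, so exposure is cumulative, and those who reach high doses are selected non-responders. Late events cannot be assigned to one dose, and during the challenge FEV1 is measured only when symptoms or PEF prompt it. All of this stands. It shapes the table and its footnotes but does not remove the need for one.

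**Conclusion.** The point holds as a gap in the planned analysis: tolerability is to inform the dose range, and nothing in the SAP relates AEs to dose or to the number exposed at a dose. On the documents' own illustration, the reported rate for one event at Dose 5 is less than a third of the rate among those exposed, and the upper limit for no events rises from 31% to 71%.

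The size rests on that illustration. The documents do not give the number who reached each dose, so a claim that only one or two people had the top dose would be conjecture. Nor is the spacing of doses stated. A Bla g 1 range of about 0.002 to 5 mcg is a 2,500-fold span, which over 7 steps gives 2,500^(1/7) = 3.06-fold per step only if the ratios are equal; the dilutions are in the Manual of Procedures.

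This is a cheap improvement worth making. It is not a flaw that invalidates the phase-level safety results, and it implies no view on which doses are appropriate.

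**What to change.** Keep the phase-level AE tables for the procedure-level question. Add to SAP 8.2 one descriptive table for each of Phases 1a, 1b and 2, with a row for the diluent and for each allergen dose, and these columns:

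1. Number who received that dose (in Phase 1b, at the Repeat Challenge Visit).
2. Number with a related AE or systemic reaction starting after that dose and before the next, within the challenge visit.
3. Number with a PEF fall of more than 20% from baseline.
4. Number with an FEV1 fall of more than 15%, out of those who had spirometry at that point.
5. Number of challenges stopped for intolerance, lung function or another safety reason, kept apart from positive responses and from completing the last dose without a response.

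Use the number who received the dose as denominator (the number measured, for FEV1), with Clopper-Pearson 95% intervals. Show events after the visit separately, by highest dose received. Footnote that exposure is cumulative and that people at the higher doses are selected non-responders. State that any conclusion on the safety of the dose range will rest on this table.

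The cost is one extra table per phase. It needs AE onset times or dose at onset on the eCRF, which should be checked first. Safety figures at the upper doses will be wider and less favourable. Dosing, visits and sample size do not change.
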